an important identified risk. Reduced haemoglobin/anaemia and reduced absolute neutrophil count/neutropenia are important potential risks. When AZD9150 is given in combination with durvalumab, there is a potential for increased frequency and/or magnitude of liver enzymes (since AST/ALT increase is an identified overlapping adverse drug reaction for both drugs; referred to as increased frequency of immune reactions in combination with durvalumab). Risks associated with other combination drugs in recently initiated studies, or studies in course of being initiated (including for example acalabrutinib, or different chemotherapy agents) are yet unknown. For a complete characterisation of each risk, see Section 6 of the IB for AZD9150, Summary of data and guidance for the Investigators.

Effects on blood neutrophils, including reduction in their number (neutropenia) is an identified risk with AZD5069. These effects have been observed at mild levels in healthy volunteers' studies. Across all respiratory studies, now completed, events suggestive of this risk occurred at both mild, moderate, but also 1 severe occurrence (event that was considered serious by the Investigator). In the ongoing D5660C00004 oncology trial so far, although reductions in peripheral blood neutrophil counts have been observed, these have been reversible, not associated with significant clinical symptoms, and not considered serious by the Investigators. Therefore, for regulatory reporting purposes that consider seriousness, events suggestive of this risk are considered expected in patients treated in respiratory indications only, and not yet in the oncology population. Host defence (infections) is a potential risk for AZD5069. However, while reduction of neutrophils in peripheral blood or sputum could have an impact on host defense with regard to infections, previous studies with AZD5069 in healthy subjects and in patients with chronic obstructive pulmonary disease, bronchiectasis, and asthma did not show an increased rate of overall infections compared with placebo. For a complete list of potential risks and their characterisation, see Section 6 of the IB for AZD5069, Summary of data and guidance for the Investigators.

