7. Has adequate organ and marrow function as defined below. Transfusions intended to elevate any parameters below solely for the intent of meeting study eligibility are not permitted.
 - Leukocytes ≥ 3000 mcL
 - Absolute neutrophil count ≥ 1500 mcL
 - Platelets $\geq 100\ 000$ mcL
 - Haemoglobin ≥ 9 g/dL
 - Total bilirubin (TBL) $\leq 1.5 \times$ upper limit of normal (ULN); TBL $\leq 3 \times$ ULN in patients with documented Gilbert's Syndrome (unconjugated hyperbilirubinaemia) or in the presence of liver metastases
 - ALT and AST $\leq 2.5 \times$ ULN if no demonstrable liver metastases or $\leq 5 \times$ ULN in the presence of liver metastases
 - Creatinine within normal limits
OR, for patients with levels above institutional normal:
 - Creatinine clearance measured by 24-hour urine collection
 ≥ 60 mL/min,
OR
 - Calculated corrected creatinine clearance ≥ 60 mL/min/1.73 m² using the Cockcroft-Gault formula (Cockcroft and Gault 1976) (see Section 8.4).
8. Women of childbearing potential and men who are sexually active with a female partner of childbearing potential must be surgically sterilised, practicing abstinence, or agree to

use 2 birth control methods before study entry, for the duration of study participation, and for 20 weeks after the final dose of study drug (180 days after final dose if patients enrolled in Arm A4); cessation of birth control after this point should be discussed with a responsible physician.

Women of childbearing potential are defined as those who are not surgically sterile (i.e., bilateral tubal ligation, bilateral oophorectomy, or complete hysterectomy) or postmenopausal (defined as 12 months with no menses without an alternative medical cause). Section 3.8.1 and Table 1 lists the methods of contraception considered adequate; note that 2 methods must be combined. Periodic abstinence, the rhythm method, and the withdrawal method are not acceptable methods of birth control.

Should a woman become pregnant or suspect she is pregnant while participating in this study, she should inform her treating physician immediately.

9. Women of childbearing potential also may not be breast feeding and must have a negative serum or urine pregnancy test within 72 hours before the start of study treatment.

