Any AE occurring before the first dose of IP will be included in the data listings but will not be included in the summary tables of AEs. Summary tables will include only AEs observed following the beginning of combination dosing up to and including 28 days after last dose. One table summarising the incidence of AE occurring from the beginning of monotherapy up to the beginning of combination therapy will be generated.

Any AE occurring within the defined 28-day follow-up period after discontinuation of IP will be included in the AE summaries. AEs occurring after the 28-day follow-up period after discontinuation of IP will be listed separately but not included in the summaries.

Haematology, clinical chemistry, vital signs, and ECG data will be listed individually by patient and suitably summarised. For all laboratory variables, which are included in the current version of CTCAE, the CTCAE grade will be calculated. Summary statistics of mean, median, standard deviation, minimum, maximum, and number of observations will be used.

Details of any deaths will be listed for all patients.

For urinalysis parameters, any qualitative assessments will be summarised for all patients using the number of patients with results of negative, trace, or positive.

Graphical presentations of safety data will be presented as is deemed appropriate. This may include, but is not restricted to, presentation of parameters against time, concentration or shift plots. Appropriate scatter plots will also be considered to investigate trends in parameters compared with baseline.

Pharmacokinetics

Plasma concentrations for each of the drug substances AZD9150, AZD5069, tremelimumab, and MEDI4736 measured within each of the combination groups with any associated metabolites will be summarised by nominal sample time.

The following summary statistics will be presented for plasma concentrations at each time point and for the following PK parameters including, AUC, AUC₍₀₋₂₄₎, AUC₍₀₋₄₈₎, AUC_(0-t), AUC_(ss), C_{max}, C_{ss max}, C_{trough}, and C_{ss min}:

- The geometric mean (calculated as $\exp[\mu]$, where μ is the sample mean of the data on a logarithmic scale)
- Coefficient of variation (calculated as $100 \sqrt{[\exp(s^2)-1]}$, where s is the standard deviation of the data on a log-scale)
- Gmean \pm standard deviation (calculated as $\exp[\mu \pm s]$)
- Arithmetic mean calculated using untransformed data
- Standard deviation calculated using untransformed data
- Minimum
- Maximum

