### 3.2.2. Dose-expansion Part B

The secondary objectives of the dose-expansion phase are to:

- Evaluate the safety and tolerability of AZD9150 and AZD5069 both as monotherapy and in combination with MEDI4736
- Assess secondary measures of efficacy (disease control rate [DCR] at 12 weeks; duration of overall response [DOR]; progression-free survival [PFS]; overall survival [OS]; and proportion of patients alive at 12 months)
- Assess the PK of AZD9150 and AZD5069 both as monotherapy and in combination with MEDI4736
- Assess the urinary pharmacokinetics of AZD9150 alone or in combination with MEDI4736
- Determine the IM of MEDI4736 in combination with AZD9150 or AZD5069
- Determine the IM of AZD9150 alone or in combination with MEDI4736
- Assess pharmacodynamic response in blood for AZD9150 and MEDI4736 (soluble PD-L1 will not be evaluated for Arms B1, B2, and B4 post the first 20 patients and for Arms B7 and B8)
- Assess tumour cell pharmacodynamics (STAT3 knockdown)
- Assess baseline circulating myeloid-derived suppressor cell (MDSC) and effect of treatment on circulating MDSCs (will not be evaluated for Arms B1, B2, and B4 post the first 20 patients and for Arms B7 and B8)
- Evaluate baseline tumour PD-L1 expression for potential correlation with drug activity or the ability to prospectively identify patients likely to respond to treatment

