#### 4.4. PHARMACODYNAMIC ENDPOINTS

The pharmacodynamic endpoints for dose-escalation Part A include the following:

- For AZD9150: Signal transducer and activator of transcription 3 (STAT3) knockdown in blood
- For MEDI4736: Soluble programmed cell death-ligand 1 (sPD-L1)
- For AZD5069: Circulating myeloid-derived suppressor cells (MDSCs)

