## Statistical Analysis Plan

### 6.2. KEY DEFINITIONS

For the purposes of this study, the term “study drug” is restricted to AZD9056, AZD9150, MEDI4736, treme, and the 4 drug combinations, AZD9056/MEDI4736, AZD9150/MEDI4736, AZD9056/MEDI4736/treme and AZD9150/MEDI4736/treme.

Study Day is the day relative to the date of the first dose of study drug in Cycle 1. If a date falls on or after the date of the first dose in Cycle 1, then the corresponding Study Day is calculated as (Study date) – (Date of first dose in Cycle 1) + 1. If a date falls before the date of first dose in Cycle 1, the corresponding Study Day is calculated as (Study date) – (Date of first dose in Cycle 1). Day -1 is the day immediately before the date of the first dose in Cycle 1.

The last dose date is defined as the last non-missing date where a non-zero dose of study drug was recorded. For patients who are ongoing at the time of an interim analysis, the last dose date will be considered the date of the most recent study visit in the database for that patient where a non-zero dose of study drug was recorded.

Unless otherwise specified, baseline is the last non-missing observation before the start of study treatment in Cycle 1.

In treatment arm A1 (AZD9150/MEDI4736), A4 (AZD9150/MEDI4736 or AZD9150/MEDI4736/treme) in dose escalation Part A, an evaluable patient must have received all 3 loading doses of AZD9150 during the 7-day Lead-in period and at least 3 additional doses during Cycle 1 as well as the MEDI4736 and treme infusion during the DLT Evaluation period or have suffered a DLT within the first 35 days of treatment. In treatment arm A2 (AZD5069/MEDI4736) in dose escalation Part A, an evaluable patient must have received all doses during the 7-day Lead-in period (i.e., 14 doses) and at least 42 additional doses as well as the MEDI4736 infusion during the DLT Evaluation period or have suffered a DLT during or before the first 35 days of treatment.

An efficacy evaluable patient is defined as a patient with unidimensional measurable disease at baseline as per the RECIST version 1.1 criteria who received at least 1 dose of study treatment.

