#### 10.1.3. Circulating Myeloid-Derived Suppressor Cells (MDSCs)

For all patients, blood samples for MDSC (5 mL), will be collected pre-dose at the specified time points to assess the treatment effect on circulating MDSCs: At screening, Day -7 of the lead-in period, Day 1 of Cycles 1, 2, 3, 5, and at the EOT visit.

For patients in Arm B1, B2, and B4 MDSC samples will not be collected after the first 20 patients. MDSC samples will also not be collected for Arms B7 and B8. Summary tables will report descriptive statistics including median results for circulating MDSC levels and the change from baseline by visit for each AZD5069 treatment group. A line plot with

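### The SAP's default baseline normally falls after the 7-day lead-in, so laboratory, vital-sign and MDSC change tables start from an on-drug value: wrong for arms B5 and B6, and most important for AZD5069 neutrophils and MDSCs

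*SAP*

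**What the plan says.** **The rule.** SAP 6.2: "Unless otherwise specified, baseline is the last non-missing observation before the start of study treatment in Cycle 1". The only analysis text that sets a different baseline is SAP 8.3.6, which takes tumour size from the last evaluable assessment before the first dose of study drug.

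**The lead-in.** Protocol 4.1.2 and 4.2.2 place a 7-day lead-in before Cycle 1. AZD9150 is infused on Days -7, -5 and -3, or AZD5069 is taken twice daily from Day -7. MEDI4736 starts on Cycle 1 Day 1.

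**The samples.** Haematology and chemistry (Protocol Table 5 footnote f) and vital signs (Protocol 5.4.4) are taken at screening, predose on Day -7 and again predose on Cycle 1 Day 1. MDSCs are collected predose "At screening, Day -7 of the lead-in period, Day 1 of Cycles 1, 2, 3, 5, and at the EOT visit" (SAP 10.1.3).

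**The tables.** SAP 11.4 reports laboratory change from baseline by visit, and shifts from baseline to the maximum post-baseline CTCAE grade. SAP 11.5 does the change summary for vital signs. SAP 10.1.3 plans "descriptive statistics including median results for circulating MDSC levels and the change from baseline by visit for each AZD5069 treatment group".

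**The adverse event reference point.** Protocol 8.10: "Summary tables will include only AEs observed following the beginning of combination dosing up to and including 28 days after last dose". The same section adds one separate table for the lead-in. SAP 11.3 counts treatment-emergent events from the first dose of study drug and also lists a lead-in AE table.

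**The concern.** A baseline taken after a week of treatment absorbs whatever that week did. If AZD5069 lowers neutrophils or MDSCs within days and the level then holds, the change table shows little or nothing.

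The two measures most exposed are ones the documents care about. Protocol 1.3.2 says: "Effects on blood neutrophils, including reduction in their number (neutropenia) is an identified risk with AZD5069". SAP 4.4 names circulating MDSCs as the AZD5069 pharmacodynamic endpoint, and SAP 3.2.2 makes the "effect of treatment on circulating MDSCs" a Part B secondary objective.

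In B6 (AZD5069 alone) the change table compares one on-drug value with another, so it cannot show the effect of starting the drug. In B5 (AZD9150 alone) the same holds for laboratory tests and vital signs.

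**Working it through.** **Step 1. Which value does the rule select?**

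| Measure | Pre-drug sample available | Value the rule normally selects | Own baseline in the SAP |
|---|---|---|---|
| Laboratory tests | Screening, Day -7 predose | Cycle 1 Day 1 predose | No |
| Vital signs | Screening, Day -7 predose | Cycle 1 Day 1 predose | No |
| MDSCs | Screening, Day -7 predose | Cycle 1 Day 1 predose | No |
| ECG, Arm B8 | Screening, Day -7 predose | Cycle 1 Day 1 predose | No |
| ECG, other arms | Screening | Screening (the Cycle 1 Day 1 ECGs are post-dose, Protocol 5.4.3) | Not needed |
| sPD-L1 | Cycle 1 Day 1 predose, before any MEDI4736 | Cycle 1 Day 1 predose | Not needed |
| Tumour size | Before first dose | Not applicable | Yes, SAP 8.3.6 |

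The word normally is needed. If the Cycle 1 Day 1 sample is missing, the rule falls back to Day -7 or screening, and patients in one table then have different kinds of baseline.

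**Step 2. How much drug comes before it?**

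- AZD5069: 7 days × 2 = 14 doses, the figure SAP 6.2 itself gives for the lead-in. Protocol 5.4 allows laboratory samples up to 2 days early; before a Day -2 morning sample, 5 days × 2 = 10 doses have been taken.
- AZD9150, weekly 3 mg/kg arms: 3 × 3 = 9 mg/kg in the lead-in against 4 × 3 = 12 mg/kg in Cycle 1; 9/21 = 43% of the two together.
- AZD9150, Arm B8: 3 × 200 = 600 mg against 2 × 400 = 800 mg; 600/1400 = 43%.

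**Step 3. Effect on reported change.** Let f be the share of the total change that arises in the lead-in and persists. Then reported absolute change = (1 − f) × total change. The documents do not give f, so the whole range is shown. The start is the entry floor in Protocol 3.1.1 ("Absolute neutrophil count ≥ 1500 mcL"). The end points are the Grade 3 and Grade 4 neutrophil limits in Protocol 7.7.3 (1000 and 500).

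| Assumed f | 1500 to 1000 (total −500) | 1500 to 500 (total −1000) |
|---|---|---|
| 0% | −500 | −1000 |
| 25% | −375 | −750 |
| 50% | −250 | −500 |
| 75% | −125 | −250 |
| 100% | 0 | 0 |

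Protocol 8.6 also calls for percent change in pharmacodynamic variables. With L the change by Cycle 1 Day 1 and T the total, both relative to Day -7, the reported percent change is (1 + T)/(1 + L) − 1. For an assumed T of −50%, it is −44.4%, −28.6% or 0% for L of −10%, −30% or −50%.

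**Step 4. Effect on shift tables.** Assume neutrophils of 1600 on Day -7, 900 at Cycle 1 Day 1 predose, and a later minimum of 1200. Under SAP 6.2 the 900 (Grade 3, below 1000) is the baseline. It cannot count as the post-baseline maximum grade, and the reported change at the later minimum is 1200 − 900 = +300. From the Day -7 value it is 1200 − 1600 = −400, and the Grade 3 value counts as post-baseline. Since entry requires at least 1500, a Grade 3 baseline would have arisen after eligibility was met.

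**Step 5. Which arms?** In combination arms MEDI4736 is added on Cycle 1 Day 1, so the selected value is a genuine pre-combination reference. In B5 and B6 nothing is added, and it has no such meaning.

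**The case against.** The Cycle 1 anchor looks deliberate. SAP 6.2, 7.6 and 11.2 tie Study Day, prior medication, treatment duration and time on study to Cycle 1. SAP 8.3.6 departs from it where a pre-drug value was wanted, and Protocol 8.10 starts AE summaries at combination dosing. For combination arms, MDSCs included, this stands as a case for one valid view. It does not reach B5 and B6, and it does not show what the lead-in drug did.

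Lead-in effects are not hidden. By-visit values, listings, the MDSC levels plot by study day, the neutrophil-to-lymphocyte plots from Day -7 and the lead-in AE table would all show something. In Step 4 the Grade 3 value is moved to the baseline category, not lost. This also stands, and it limits the harm. It does not correct the change and shift tables. The AE route is only partial, because Protocol 6.4.6 limits reporting of mandated laboratory deterioration to events that meet SAE criteria or lead to discontinuation.

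The illustrations may overstate the effect. Protocol 1.3.1 expects modest neutrophil reductions, and Protocol 1.3.2 describes those seen in this trial as reversible and not considered serious. That is fair; the figures show the mechanism and are not a forecast.

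A reader might infer that every safety and efficacy change table is biased, that neutropenia would go unseen, or that all ECG baselines are on-drug. The documents support none of these. Outside B8 the rule already selects the screening ECG, and neutropenia DLTs use absolute counts from the first lead-in dose.

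**Conclusion.** The point holds. For laboratory tests, vital signs and MDSCs the default baseline is normally an on-drug value, and change and shift tables leave out effects that arise in the lead-in and persist. This is wrong for B5 and B6 (12 efficacy-evaluable patients planned in each) and matters most for AZD5069 neutrophils and MDSCs. In combination arms the baseline answers one legitimate question and leaves the effect of the lead-in drug unreported in the change tables.

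The direction is clear but the size is not. Anywhere from all to none of a persisting effect could be reported, depending on f. For AZD9150 platelets f may be small: Protocol 1.2 cites preliminary data from another study with only mild thrombocytopenia at about Week 5. For vital signs no effect is shown. MDSC change tables cover AZD5069 groups only, and sampling stops after the first 20 patients in B2 and B4.

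The objective response rate, tumour size, DLTs and Hy's Law tables are unaffected, and the affected summaries are descriptive. The conclusion assumes that sampling follows the schedule and that the table shells, kept in a separate document, do not set another baseline.

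**What to change.** In SAP 6.2:

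- For laboratory tests, vital signs and MDSCs, define baseline as the last non-missing value before the first dose of any study drug: Day -7 predose, or screening if that is missing.
- Keep Cycle 1 Day 1 predose as baseline for sPD-L1 and MEDI4736 ADA.
- In combination arms, keep Cycle 1 Day 1 predose as a second, pre-combination reference.
- For ECG, change the baseline in Arm B8 only, to Day -7 predose, and state whether the B8 post-infusion ECGs on Day -7 enter the QTc change tables.

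Cost: reprogramming the change and shift tables and one added set of combination-arm tables. The samples are already scheduled.

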## Statistical Analysis Plan

### **6.3. MISSING DATA**

There will be no imputation of missing data unless specified. Imputation methods for missing target lesion data are included in Section 8.3.6 of this SAP.

### **6.4. SUBGROUPS**

No subgroup analyses are planned.

## Statistical Analysis Plan

### **7. DEMOGRAPHIC, OTHER BASELINE CHARACTERISTICS AND MEDICATION**

#### **7.1. PATIENT DISPOSITION AND WITHDRAWALS**

All patients who provide informed consent will be accounted for in this study.

The disposition of patients who provided informed consent will be summarized using the All Patients (i.e., to include screen failures) and Full Analysis sets. The total number of patients screened, the number and percentage of patients who were assigned to treatment, and the number and percentage of patients who were screen failures will be included along with the reasons for screen failure. The number and percentage of patients who did not receive treatment and the number and percentage of patients who did receive treatment will be summarized by treatment group.

The disposition of patients who received treatment will be summarized using the Safety Set. The number and percentage of patients in each treatment group, the reason for treatment discontinuation and the reason for study discontinuation will be included.

The number and percentage of patients in each analysis set (i.e., Efficacy, PK, Pharmacodynamics) will be summarized by treatment group using the Safety Set as the denominator. For patients in the Full Analysis Set, the reasons for exclusion from each of the analysis sets mentioned above will be listed.

For all treated patients, the planned treatment arm, the date of all disposition events, the standardized disposition term, and the total number of treatments of each study drug will be listed. For patients not assigned or randomized to study drug, the reasons for screen failure will be listed.

#### **7.2. PROTOCOL DEVIATIONS**

Protocol deviations will be captured in eCRF. These protocol deviations are classified into the following categories: prohibited use of concomitant medications, dosing, enrollment, laboratory, non-compliance, visit schedule and other. Important deviations that may affect PK, PDN, Safety, and Efficacy analyses will also be identified and used to exclude patients from their respective Analysis Sets.

All protocol deviations will be summarized by category and treatment group. All protocol deviations will be listed.

## Statistical Analysis Plan

### 7.3. DEMOGRAPHIC AND OTHER BASELINE CHARACTERISTICS

Age (years) will be calculated as the number of years between the date of birth and the date of informed consent.

Age at screening = (informed consent date – date of birth +1)/365.25 and truncated to complete years.

If height is recorded in inches (in), then height will be summarized in cm using the following conversion:

$$\text{Height (cm)} = \text{Height (in)} \times 2.54$$

If weight is recorded in pounds (lb), then weight will be summarized in kilograms (kg) using the following conversion:

$$\text{Weight (kg)} = \text{Weight (lb)} \times 0.4536$$

Demographic and baseline characteristic data (sex, race, ethnicity, age (yr), height (cm), weight (kg)) will be summarized by treatment group for subjects in the Safety Set.

All demographic and baseline characteristic data will also be listed, including the protocol version (captured in eCRF) under which the patient screened and the date of informed consent.

